8.1.7 Evaluation of BRAF-MDQ

The BRAF MDQ (Bristol Rheumatoid Arthritis [RA] Fatigue Multi-Dimensional Questionnaire)¹⁵ was developed to assess the overall experience and impact of RA fatigue, and its different dimensions.

Items scored 0–3, except for items 1 (scored 0–10), 2 (scored 0–7), and 3 (scored 0–2). A total fatigue score is obtained by summing the 20 item scores. Subscale items are summed to produce scores for physical fatigue, living with fatigue, cognitive fatigue, and emotional fatigue. Instructions for missing data are that only 3 questions may be omitted in total, questions 1 and 2 must be completed, and only 1 question may be omitted from each subscale (replaced with patient's average score for that subscale).

Higher scores reflect greater severity. Total fatigue score is 0–70; subscale scores are physical fatigue 0–22, living with fatigue 0–21, cognitive fatigue 0–15, and emotional fatigue 0–12.

Figure 2: BRAF-MDQ Score table

Dimension	Questions	Range	Score
Physical	1 NRS fatigue	0-10	
	2 How many days?	0-7	
	3 How long on average has each episode of fatigue lasted?	0-2	
	4 Have you lacked physical energy because of fatigue?	0-3	
Physical total (0-22)			
Living	5 Has fatigue made it difficult to bath or shower?	0-3	
	6 Has fatigue made it difficult to dress yourself?	0-3	
	7 Has fatigue made it difficult to do your work or other daily activities?	0-3	
	8 Have you avoided making plans because of fatigue?	0-3	
	9 Has fatigue affected your social life?	0-3	
	10 Have you cancelled plans because of fatigue?	0-3	
	11 Have you refused invitations because of fatigue?	0-3	
	Living total (0-21)		
	12 Have you lacked mental energy because of fatigue?	0-3	
	13 Have you forgotten things because of fatigue?	0-3	
	14 Has fatigue made it difficult to think clearly?	0-3	
Cognition	15 Has fatigue made it difficult to concentrate?	0-3	
	16 Have you made mistakes because of fatigue?	0-3	
	Cognition total (0-15)		
	17 Have you felt you have less control because of fatigue?	0-3	
	18 Have you felt embarrassed because of fatigue?	0-3	
Emotion	19 Has being fatigued upset you?	0-3	
	20 Have you felt down or depressed because of fatigue?	0-3	
	Emotion total (0-12)		
	BRAF-MDQ Total score (0-70)		

Missing data is handled as follows:

- Questions 1 and 2 are compulsory.
- Only 1 question may be missing from each dimension (maximum of 3 in the overall BRAF-MDQ).
- Replace the missing question score with the average score for that dimension.
- For the Physical Fatigue dimension, a weighted average score is used to account for the varying item score ranges: Total the 3 completed scores, divide by the total max possible score for those 3 questions, then multiply by the maximum score possible for all 4 questions (22).

For example:

- Q1 is 10/10, Q2 is 6/7, Q3 is missing, and Q4 is 2/3.
- Total completed score =18.
- Divide by total max possible for those 3 questions (10+7+3) i.e. 18/20 = 0.9 weighted average.
- Multiply by the max possible score for all 4 questions i.e. 0.9 x 22 = 19.8.
- Physical Function score is thus imputed as 19.8.

8.1.8 *Evaluation of SF-36 Summary Functions and Components*

The SF-36 is composed of 36 items measuring 8 health concepts: Physical Functioning, Role-physical, Bodily Pain, General Health, Vitality, Social Functioning, Role-emotional, and Mental Health. These 8 scales form 2 summary scores: (1) Physical Component Summary (PCS) and (2) Mental Component Summary (MCS). Scoring conventions for the SF-36 scales and components are documented in “SF Health Outcomes TM Scoring Software User’s Guide”¹⁶.

8.2 Handling of Procedures, Conditions and Intra-articular Injections of Joints

Joints may have been undergone procedures (e.g., fusion/ankylosis, synovectomy, steroid injection, and amputation) due to worsening RA during the study. Joint status is adjusted according to the following rules:

- If a joint undergoes procedure on or before the start of study drug, then for this joint both tenderness and swelling will be considered as ‘not present’ for all visits.
- If a joint undergoes procedure due to RA involvement and occurs after the start of study drug, then for this joint both tenderness and swelling will be considered as ‘present’ for all visits on or after the procedure.
- If a joint undergoes procedure for reason other than RA involvement and occurs after the start of study drug, then for this joint both tenderness and swelling will be considered as ‘not present’ for all visits on or after the surgery procedure date.

In addition, joint status is also adjusted for conditions and IA injection as follows:

- If a joint undergoes other procedures or conditions at any visit, then for that joint both tenderness and swelling will be considered as ‘not present’ at that particular visit.
- If an intra-articular injection occurs, then for that joint both tenderness and swelling will be considered as ‘present’ at that particular visit and all subsequent visits.

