3.3.2 Exclusion Criteria

1. Target Disease Exceptions

- a) Subjects with:
 - i) documented juvenile rheumatoid arthritis
 - ii) Felty's syndrome
- b) Biologic treatments other than TNF inhibitors.
- c) Subjects who are currently receiving immunomodulators other than methotrexate.
- d) Subjects who have been treated with Intramuscular (IM) or Intra-articular glucocorticosteroids within 4 weeks of randomization (Day 1).

Oral steroid use is permitted, but only if ≤ 10 mg/day of prednisone (or prednisone equivalents)

2. Medical History and Concurrent Diseases

- a) Subjects at risk for tuberculosis (TB). Specifically, subjects with:
 - i) Current clinical, radiographic or laboratory evidence of active TB.
 - ii) A history of active TB within the last 3 years even if it was treated.
 - iii) A history of active TB greater than 3 years ago unless there is documentation that the prior anti-TB treatment was appropriate in duration and type.
 - iv) Therapy for Latent TB which has not been completed as per local country guidelines.
 - v) This exclusion criteria was a duplicate of Exclusion 2b and was removed in Amendment 5, bullet is being left to maintain numbering.
- b) Subjects with any bacterial infection within the last 60 days prior to screening (enrollment), unless treated and resolved with antibiotics, or any chronic or history of recurrent bacterial infection (such as chronic pyelonephritis, osteomyelitis, and bronchiectasis).
- c) Subjects who have a history of systemic fungal infections (such as histoplasmosis, blastoplasmosis, or coccidioides).

- d) Subjects with herpes zoster symptoms that resolved less than 60 days prior to screening visit (enrollment).
- e) Subjects with evidence (as assessed by the investigator) of active or latent bacterial or viral infection at the time of potential enrollment, including subjects with history or evidence of Hepatitis B or Hepatitis C, history or evidence of Human Immunodeficiency Virus (HIV) infection.
- f) Subjects with autoimmune disease other than RA (eg, Systemic lupus erythematosus [SLE], multiple sclerosis [MS], vasculitis).
- g) Significant concurrent medical condition at the time of screening or baseline visit, including, but not limited to, the following:

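### SAP 8.2 scores some joints that cannot be assessed after baseline as healed, and read literally erases any joint ever injected with steroid before the study

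*SAP*

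**What the plan says.** SAP 8.2 adjusts joint status by five bullets, called rules 1 to 5 here in the order in which they appear. They follow an introductory sentence: "Joints may have been undergone procedures (e.g., fusion/ankylosis, synovectomy, steroid injection, and amputation) due to worsening RA during the study".

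- **Rule 1.** "If a joint undergoes procedure on or before the start of study drug": not tender and not swollen at all visits.
- **Rule 2.** "If a joint undergoes procedure due to RA involvement and occurs after the start of study drug": tender and swollen at all visits from the procedure on.
- **Rule 3.** "If a joint undergoes procedure for reason other than RA involvement and occurs after the start of study drug": not tender and not swollen at all visits from the procedure on.
- **Rule 4.** "If a joint undergoes other procedures or conditions at any visit": not tender and not swollen at that visit. The term for conditions is not defined.
- **Rule 5.** "If an intra-articular injection occurs, then for that joint both tenderness and swelling will be considered as" present, at that visit and every later one.

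No rule adjusts the baseline count when a joint is affected later, and none removes a joint from the count or prorates. SAP 8.3 classifies a subject with an on-study intra-articular or intramuscular injection as a non-responder from that point. Protocol 3.3.2 excludes subjects given intramuscular or "Intra-articular glucocorticosteroids within 4 weeks of randomization (Day 1"), so subjects with older injections can enter.

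**The concern.** Tender and swollen counts are both mandatory for ACR20 and ACR70, the co-primary endpoints, and they enter DAS28, CDAI, SDAI and Boolean remission. SAP 8.1.1 measures improvement against the Day 1 value. If a joint active on Day 1 is later set to inactive because it cannot be judged, the formula cannot tell it from a joint that healed.

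This departs from how the SAP treats missing information elsewhere. A binary response that cannot be determined becomes a non-response (8.5.1), HAQ-DI divides by the categories answered (8.1.5), BRAF-MDQ prorates (8.1.7), and an MRI score with more than 20% of sites missing is set to missing (7.5.2.1). Only here does lack of an assessment become a favourable value.

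Rule 1 raises a different problem. Steroid injection is among the listed procedures and no look-back limit is given. A joint injected long before the study, and now active and assessable, would be dropped from measurement at every visit. Eligibility requires at least 6 tender and 6 swollen joints. If that is judged on joints as examined, the analysis baseline can be lower.

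**Working it through.** **Inputs.** Entry minimum of 6 swollen and 6 tender joints on the 66/68 count (Protocol 3.3.1, criterion 2e). Percent improvement = 100 × (baseline − post) / baseline, with 20%, 50% or 70% required in both counts plus 3 of 5 other measures (SAP 8.1.1). DAS28 joint terms 0.56 × √TJC28 + 0.28 × √SJC28 (SAP 8.1.2). CDAI and SDAI add the two 28-joint counts directly (SAP 8.1.3 and 8.1.4).

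**The plan's own figure.** SAP 8.2 states none. The nearest is the roughly 90% ACR70 power in Protocol 8.1 (82 per arm, 2.5% versus 19.5%, two-sided 0.05). A continuity-corrected normal approximation gives 90.6%; without the correction it is 94.3%. The stated figure reproduces, and nothing below shows it to be wrong.

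**Rules 3 and 4, percent change.** Take a joint both tender and swollen at baseline, with no true change in any joint.

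| Baseline count | One joint zeroed | Joints zeroed to meet the joint-count part of ACR20 / ACR50 / ACR70 |
|---|---|---|
| 6 | 1/6 = 16.7% | 2 / 3 / 5 |
| 10 | 1/10 = 10% | 2 / 5 / 7 |
| 20 | 1/20 = 5% | 4 / 10 / 14 |

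Two joints at baseline 6 give (6 − 4)/6 = 33.3%.

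**Rules 3 and 4, index scores.** For a joint among the 28 that is both tender and swollen, the DAS28 joint terms fall by 0.84 × (√6 − √5) = 0.18 at counts of 6, and by 0.84 × (√10 − √9) = 0.14 at counts of 10. CDAI and SDAI each fall by 1 + 1 = 2 points.

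**Rule 1.** The joint is zero at baseline and at follow-up, so it contributes no change. It does alter the denominator. Suppose the true count falls from 8 to 6 (25%) and two joints are hidden:

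- if the hidden joints stay active, the analysis sees 6 to 4, or 33.3%;
- if the hidden joints are the two that improved, it sees 6 to 6, or 0%.

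The direction is therefore unpredictable for percent change. For absolute scores it is not: removing an active joint among the 28 can only lower DAS28, CDAI and SDAI at a visit and make Boolean remission (both 28-joint counts at most 1) easier.

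**Rule conflicts.** Steroid injection is a listed procedure and also the subject of rule 5. An injection before first dose is inactive under rule 1, but rule 5 has no start date and makes it active. An injection after first dose for a non-RA reason is inactive under rule 3 and active under rule 5. No order of precedence is given.

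**Check of remedies.** Prorating only the follow-up swollen count does not help. One joint: 5 × 66/65 = 5.08, and (6 − 5.08)/6 = 15.4%, against 16.7%. Two joints: 4 × 66/64 = 4.125, and (6 − 4.125)/6 = 31.3%, against 33.3%. Leaving the two joints out at both visits gives 4 to 4, or 0%. Prorating both counts by the same factor also gives 0%.

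**The case against.** The rules are not uniformly lenient. The disease-driven events are handled conservatively: rule 2 scores RA-related procedures as active, rule 5 does the same for injections, and SAP 8.3 adds non-response for an on-study injection. A reader might infer that every joint that becomes unassessable after baseline is scored as healed. The documents do not support that; only non-RA procedures and other procedures or conditions are. This stands.

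A reader might also infer that rule 1 manufactures response. It does not, because the joint is zero at baseline too. In addition, the introductory sentence ties the listed procedures to worsening RA during the study, and injections have their own rule, so the authors may not have meant rule 1 to cover old injections. That is a fair reading of intent. But rule 1 expressly covers procedures before first dose, no other list of procedures is offered, and a programmer following the text would zero those joints.

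Finally, a reader might infer a loss of power. Adding one false ACR70 responder to placebo alone lowers exact power of the uncorrected chi-square test from 96.8% to 93.1%. The same rules apply in every arm of a double-blind trial: one false responder in each arm gives 95.8%, and one in the active arm alone gives 98.2%. Nothing singles out placebo, and with baseline 6 and no true change it takes five zeroed joints, plus 70% improvement in 3 of 5 other measures, to make an ACR70 responder. No power figure should be attached to this point.

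**Conclusion.** The point holds in a limited form. Rules 3 and 4 turn a joint that was active at baseline and could not be judged later into an improvement: 16.7% per joint at the entry minimum, less at higher counts, with two joints enough for the joint-count part of ACR20 at baseline 6. Rule 1, on its literal wording, hides active joints injected before the protocol's 4-week window. The effect on percent change can go either way, while absolute scores are lowered and Boolean remission made easier. The overlaps of rules 1 and 3 with rule 5 let two programmers derive different counts from the same data.

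The percentages assume joints that are both tender and swollen at baseline and no true change elsewhere. The documents give no frequency of such events. Over 12 weeks they are probably few, so no change in response rate or power can be derived. This is a minor but clear defect in a derivation rule, worth correcting because correction is nearly free.

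**What to change.** Amend SAP 8.2 before unblinding:

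- **Rules 3 and 4:** treat the joint as non-evaluable and leave it out of both the baseline and the follow-up count when computing change. Where an absolute score is needed, prorate both counts to the full joint set. Define what counts as a condition.
- **Rule 1:** limit it to joints that cannot be assessed, such as fused, replaced or amputated joints. Score joints injected before the 4-week exclusion window as examined.
- **Precedence:** state which rule applies when an injection falls under rule 1 or 3 as well as rule 5, and where rule 4 ends and rules 2 and 3 begin.

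The cost is a few sentences and a small change to the joint-count derivation: the baseline used for change would depend on which joints are evaluable at each visit. No extra assessments are needed.

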8.3 Determination of Responder Data

Subjects who receive 1 or more IA or IM injection during the double-blind period of study will be classified as ACR non-responder on and after the time of the first IA or IM injection and up to the end of the double-blind period. Subjects who receive a high oral steroids course that is defined as the use of either any oral dose (equivalent of prednisone) higher than baseline (Day 1) use for ≥ 1 day or any oral dose (equivalent of prednisone) $>10\text{mg/day}$ for ≥ 1 day will be counted as non-responder at all visits subsequent to the date of dose that is higher than the baseline dose.

Subjects who increase MTX use (versus baseline) during the double-blind period will be counted as non-responder at all visits subsequent to the earliest date of increased MTX dose.

Subjects who receive any DMARDs (other than MTX) during the double-blind period will be counted as non-responder at all visits subsequent to the earliest date of DMARDs.

These rules will apply to binary endpoints including ACR20/50/70, DAS28-CRP <2.6, DAS28-ESR <2.6 and remission status defined by CDAI, SDAI and Boolean definition.

